6.5 Device deficiency

Device deficiency refers to deficiency of a medical device in identification, quality, durability, reliability, safety or performance. Medical device deficiencies include malfunction, misuse or use error and inadequate labeling.

The investigator shall record the discovered device deficiencies during the clinical investigation and analyze the cause of the event together with the sponsor, form a written analysis report, and propose a suggestion on continuation, suspension or termination of the investigation, which will be reported by the medical device clinical investigation management department to the Ethics Committee for review.

Both investigators and subjects can make a complaint against the treatment product and control product at any phase of the clinical study.

CHAPTER 7: MISCELLANEOUS CONSIDERATIONS

7.1 Trace to the source

Source data refers to original record of clinical findings, observations, and other activities in the clinical investigation, as well as all information in its approved copy, which can be used for clinical investigation reconstruction and evaluation. This clinical investigation includes: name, date of birth and gender of subjects; investigation identification code, CIP number, name of the investigational device; start date of subjects screening or enrolling; investigational device use date and quantity; signature of investigators; serious adverse events and handling information; date of collection, outcomes and date of report of laboratory specimens, signature of inspector; signature of CRA.

A source file is a printed file, a video file, or an electronic file containing source data. Informed consent form, subjects screening form and enrollment log, subject identification code list, medical documents of subjects (such as medical records or investigation medical records, including physical and chemical examination reports), investigational device use records, lab records, serious adverse event report and memo. The source file is the first-hand source of clinical investigation data records. Any observations and examination results in the clinical investigation shall be recorded the source file in a timely, accurate, complete, standardized and authentic manner.

7.3 Discontinuation of the study

A study participant may be discontinued from the study if the investigator believes that it is not safe for the participant to continue. And subjects can withdraw from the study at any time

The sponsor should ensure that all investigators in the clinical investigation strictly follow the CIP and promptly point out when the investigation sites and investigators do not observe relevant laws, the GCP and this CIP and give a timely correction; if the situation gets worse or the inobservance remains uncorrected, the sponsor should terminate the clinical investigation, and report to the local provincial food and drug administration, and China Food and Drug Administration (CFDA).

7.4 Protocol deviation and violation

Deviations from the CIP are mainly manifested as the following:

- Loss to follow up;
- Subjects do not meet the inclusion/exclusion criteria;
- Investigators or subjects are not in strict compliance with the CIP or subject compliance is poor;
- Investigation is terminated due to adverse events.

If there is a deviation from the CIP during investigation, the investigator shall promptly notify the sponsor, the investigation sites and ethics committee.

7.5 Protocol amendments

Before clinical investigation, the CIP will be discussed and revised jointly by investigators and implementers who will sign the final copy and submit it to the ethics committee for approval before implementation.

If there is a problem with the CIP during practical implementation of the clinical investigation, a revision is necessary. The plan of revision shall be proposed to the implementer for a multi-center discussion. After then, the responsible unit will carry out revision and submit the revised CIP in a written form to the implementer and investigation units for signing. Finally, send it to the ethics committee again for approval before implementation.

If new data important related to the product for verification is found, the informed consent form must be modified and sent to the ethics committee for approval.

CHAPTER 8: STATISTICAL CONSIDERATIONS

As a pilot study to evaluate the feasibility and safety of ncMCE, the sample size was not calculated [19]. Considering the capsule endoscopy volume of Shanghai Hospital during the pandemic, we planned to recruit 40 patients into two groups. Basic characteristics were presented as means with standard deviations for continuous variables such as age, body mass index (BMI), and percentages for binary variables including sex, medical history, and symptoms. Quantitative data were summarized with parametric statistics, mean and standard deviation, or nonparametric statistics, median, and interquartile range (IQR), whereas categorical data were presented as Under the condition of normal distribution and homogeneity of variance, variance analysis was used to compare the difference in mean between groups, while a K-W test was used to compare the difference in distribution between groups and Fisher' s test was used to compare the two and disordered multi-classification data of subjects under the condition that homogeneity of variance was not satisfied. All reported Pvalues are two-sided and differences that reached $P < 0.05$ were considered statistically significant. Statistical analyses were performed with SPSS (version 22.0, SPSS Inc., Chicago, Illinois, United States).

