2.1 Introduction and rationale

COVID-19, a respiratory disease that spreads via direct contact or through droplet transmission, has caused a major disruption in the healthcare system since it was first identified in 2019 [1]. Endoscopic procedures during the pandemic were divided into urgent endoscopy, semi-urgent endoscopy, and elective endoscopy, with the aim of preventing infection among healthcare professionals and providing necessary medical services [2]. For patients who required urgent gastroscopy, the face-to-face contact with endoscopists, aggressive suctioning, and coughing [3] during examination brought opportunities for transmission. Considering the reduced endoscopy volume in most endoscopy departments, diagnosis of patients who needed semi-urgent endoscopy and elective endoscopy may have been delayed [4]. Therefore, focusing on how to return to gradually return to provision of routine endoscopy services while maintaining safety for endoscopists deserves attention [5]. Capsule endoscopy provides a great view of the gastrointestinal tract through use of a miniature, pill-sized camera and it is as accurate as other gastrointestinal endoscopy modalities [6]. Its unique advantages include single use, excellent tolerance, and minimal medical staff requirement, which reduces the risk of exposure to pathogenic microorganisms and cross-infection [7] and makes it an appropriate method for examining and triaging an endoscopy department during the COVID-19 pandemic [8]. However, capsule endoscopy cannot be used to avoid face-to-face contact between endoscopists and patients who have asymptomatic COVID-19 cases [9]. Herein, we describe a novel noncontact magnetically controlled capsule endoscopy (ncMCE) system using a remote control system to separate endoscopists and patients physically, which was developed and tested in our medical center [10,11]. The objective of the present study was to evaluate the feasibility and safety of ncMCE for gastric examination.

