
4.3 Study outcomes

4.3.1 Primary efficacy outcome

The primary endpoints were feasibility assessed by completion rate (CR) and safety evaluated by the occurrence of AE. CR was defined as complete observation of the cardia, fundus, body, angulus, antrum, and pylorus of the stomach with no technical failure. Technical failure included incomplete observation, direct contact in the ncMCE group, and examination discontinuation. The safety of ncMCE was evaluated 2 weeks after the procedure for any AEs, such as infection with SARS-CoV-2 and capsule-related AEs including abdominal pain, nausea, vomiting, and capsule impaction or retention. In the current study, the endoscopist was continuously monitored for infection until 2 weeks after the last examination.

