4.3.2 Secondary efficacy outcomes

Secondary endpoints included maneuverability score, pre-procedure perception and post-procedure satisfaction of patients, gastric examination time (GET), and diagnostic yield (DY). The maneuverability of the ncMCE system was evaluated with a questionnaire that consisted of signal transmission quality (stability and fluency), endoscopist comfort (strength needed to control joysticks and degree of fatigue), visualization of gastric mucosa (whether the mucus, foam in the stomach, and gastric fullness affected observation of gastric mucosa) and compliance of patients (patient ability to readily and correctly follow verbal instructions to change positions to assist in optimizing gastric views). The score for each index was 1 to 5, with 1 as the worst and 5 as the best, respectively, and a total ranging from 4 to 20. All patients were asked about the comfort and acceptability of the procedure using an improved pre-procedure perception and post-procedure satisfaction questionnaire, which was reviewed ease of swallowing, pain or discomfort experienced during and after the procedure, overall tolerability and convenience of the procedure, and knowledge, necessity for, and acceptability of ncMCE (Questionnaire 1) [18]. GET was defined as the time taken for gastric examination and determined using a digital stopwatch in the ESNavi software. DY or detection rate was calculated using the following formula: number of patients with positive findings divided by the total number of patients that underwent examination.

CHAPTER 5: DATA MANAGEMENT

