5.3 Data entry and modification

Data entry and modification: The data of CRF were input by the independent double-entry method. Data managers check the data in the case report form and find out that questions are asked by clinical inspector. Data managers modify and confirm the data according to the researchers' answers, and if necessary, a clinical inspector can issue the questionnaires again.

After data entry and inspection, data managers, main researchers, bidders and statistic analysts jointly audit the data, and complete the final definition and judgment of the analysis population.

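### In the available text, completion rate and adverse events have only a between-group P<0.05 criterion, no interval, and an analysis population settled after data entry

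*Combined protocol and SAP*

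**What the plan says.** **Aim and endpoints.** Section 2.1: "The objective of the present study was to evaluate the feasibility and safety of ncMCE for gastric examination". Section 4.3.1: "The primary endpoints were feasibility assessed by completion rate (CR) and safety evaluated by the occurrence of AE". The same section lists what makes an examination a failure: "Technical failure included incomplete observation, direct contact in the ncMCE group, and examination discontinuation". It gives no target rate, margin or denominator for CR or AEs.

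**Inference.** Chapter 8 says that no sample size was calculated because this is a pilot, and plans 40 patients in two groups. Section 3.1 gives 1:1 allocation. Chapter 8 names analysis of variance, the K-W test and Fisher's test. Of the last it says that the "test was used to compare the two and disordered multi-classification data of subjects". It then sets the general rule: "All reported Pvalues are two-sided and differences that reached $P < 0.05$ were considered statistically significant". No test is assigned to CR or AEs by name. The sentence on presentation stops at "categorical data were presented as" and runs into another sentence.

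**Analysis population.** Section 5.3 describes a joint audit after data entry and inspection, in which data managers, main researchers, bidders and statisticians "complete the final definition and judgment of the analysis population". The available text names no intention-to-treat, per-protocol or safety set. The one explicit denominator belongs to a secondary endpoint, diagnostic yield (section 4.3.2): "number of patients with positive findings divided by the total number of patients that underwent examination". Section 7.4 lists loss to follow-up, ineligibility and poor compliance as deviations that must be notified, and is silent on their place in the analysis.

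**The concern.** The question is about one system: how often does ncMCE complete the examination, and how often is it followed by harm? A between-group test asks something else, namely whether the two arms differ by more than chance. With few patients that test misses large deficits, and when both arms do well it returns P=1.00 without saying how low the true completion rate, or how high the true AE risk, could still be. An interval answers the question asked.

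The analysis population is a second and separate gap. The trial is open-label, and the people who settle the population after data entry include the main researchers. With about 20 patients per arm, one exclusion visibly moves the CR. Section 5.4 requires changes to the statistical plan to be stated and justified, but for the analysis set the available text names no starting definition against which a change could be seen.

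**Working it through.** **Inputs.** N=40 (Chapter 8) at 1:1 (section 3.1) gives 40/2 = 20 per arm. Alpha is 0.05, two-sided (Chapter 8). The plan has no power or precision figure to reproduce. It gives no expected CR or AE rate, so every outcome count below is an assumption. Fisher's test is taken to apply to CR and AEs because both are binary.

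**1. What P<0.05 requires.** Suppose MCE completes 20/20 and ncMCE has k failures. All failures lie in one arm, so the two-sided Fisher P is 2 × C(20,k)/C(40,k).
- k=4 (16/20): 2 × 4,845/91,390 = 0.106
- k=5 (15/20): 2 × 15,504/658,008 = 0.047

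ncMCE must therefore fall to 15/20 before the rule registers a difference. By full enumeration of the two binomials, the power of Fisher's test is 4.3% if the true CRs are 100% and 90%, and 37.0% if they are 100% and 80%.

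**2. What an interval shows for the same data.** Newcombe's interval for d = p1 - p2 (ncMCE minus MCE), from Wilson limits (l, u) of each arm, is
- lower: d - √[(p1-l1)² + (u2-p2)²]
- upper: d + √[(u1-p1)² + (p2-l2)²]

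Wilson 95% limits are 0.5840 to 0.9193 for 16/20, and 0.8389 to 1 for 20/20.
- 16/20 v 20/20: lower = -0.20 - √[0.2160² + 0²] = -0.416; upper = -0.20 + √[0.1193² + 0.1611²] = +0.0005. That is -20.0 points (-41.6 to +0.1), with P=0.106.
- 20/20 v 20/20: 0 ± 0.1611, that is ±16.1 points, with P=1.00.
- AEs in 4/20 v 0/20, by symmetry: +20.0 points (-0.1 to +41.6), with P=0.106.

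**3. Bounds for ncMCE alone (Clopper-Pearson, two-sided 95%).** For x = n the lower limit is 0.025^(1/n). For x = 0 the upper limit is one minus that.

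| Result | Limit |
|---|---|
| CR 20/20 | lower 0.025^(1/20) = 83.2% |
| CR 19/20 | lower 75.1% |
| CR 18/20 | lower 68.3% |
| AE 0/20 | upper 100 - 83.2 = 16.8% |
| AE 1/20 | upper 100 - 75.1 = 24.9% |

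**4. Analysis set.** Section 4.3.1 already makes incomplete and discontinued examinations failures, so these cannot leave the CR on that ground. A failed patient could still be removed as ineligible or poorly compliant (section 7.4). One such removal turns 19/20 (lower limit 75.1%) into 19/19 (0.025^(1/19) = 82.4%).

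**5. Unknown AE status.** Suppose 2 of 20 ncMCE patients cannot be reached at 2 weeks and the other 18 have no AE. Counting the two as event-free gives 0/20, upper limit 16.8%. Among patients with known status it is 0/18, upper limit 1 - 0.025^(1/18) = 18.5%. Counting both as events gives 2/20 = 10%, upper limit 100 - 68.3 = 31.7%.

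**The case against.** **The P<0.05 sentence only defines statistical significance.** A reader might infer that the plan will take P>0.05 as showing feasibility or safety. No section says so, and section 4.3.1 can be read as describing CR without testing it. This stands. The point is that the stated method does not bound the endpoints, not that the plan draws a false conclusion from it.

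**Text is missing.** The categorical-data sentence breaks off where the presentation of CR and AEs would be described, and some pages are not in the available text. This stands too: the absence of an interval, or of an earlier analysis set, is a statement about what can be read.

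**It is a pilot, and a reader can compute limits from n/N.** Pilot status explains why no sample size was calculated, and none is asked for here. It makes estimation more relevant. That limits can be computed afterwards does not mean that the conclusions will rest on them.

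**Counting direct contact as a failure looks one-sided.** Only the ncMCE arm can fail in this way, and a reader might call the comparison flawed. The definition is deliberate: physical isolation is what distinguishes ncMCE (Appendix 1), and the rule can only lower its CR. It is not an error. Showing the difference without this component is optional.

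**Exclusions are already limited.** Section 4.3.1 counts incomplete and discontinued examinations as failures, and section 5.2 has completion judged by a blinded researcher. Both are real safeguards. They leave open patients excluded for ineligibility or poor compliance, those randomised but never examined, and those without 2-week AE follow-up.

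**Conclusion.** The point holds within these limits and should be fixed. In the available text, the only inferential method for two primary endpoints about ncMCE itself is a between-arm test. Against a perfect MCE arm, that test stays silent until ncMCE has five failures in 20. Perfect results would still be compatible with a true CR as low as 83.2% or a true AE risk as high as 16.8%. The population on which these rates rest is completed after data entry, with the three open groups of patients named above.

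The figures assume 20 per arm, illustrative counts, and Fisher's test for binary data by inference. Three stronger readings are not supported: that the plan equates non-significance with success, that it certainly contains no interval, and that failed examinations may be dropped simply for being incomplete. Nor do the documents show that outcomes by arm have been analysed when the population is settled; section 5.3 describes a data audit. Confidence is medium because of the cut-off sentence.

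**What to change.** 1. **Chapter 8.** For CR, and for patients with at least one AE, report n/N with an exact (Clopper-Pearson) 95% CI per arm and a Newcombe 95% CI for the difference. Base the feasibility and safety conclusions on these intervals.
2. **Section 5.3.** Fix the sets before outcome data by arm are reviewed, and state the date, since section 3.1 reports recruitment in the past tense. CR: all randomised patients, with examinations discontinued or never started counted as not complete. AEs: all randomised patients who began the study procedure, with its start defined. State that deviations under section 7.4 do not remove a patient from either set.
3. **Missing AE status.** Report the number per arm with unknown 2-week status, give the AE rate among those with known status, and add a sensitivity analysis counting the unknowns as events. Report the endoscopist's infection monitoring on a separate line: one endoscopist served both arms (section 5.2), so an infection may not be attributable to an arm.
4. **Optional.** Show the between-arm CR difference also without the direct-contact component, keeping that component in the primary ncMCE CR.

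Cost: some wording and a few extra lines of analysis, with no extra patients. The downside is that the intervals will be wide and the conclusions less favourable.

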3.1 Study Population

This study was a pilot, open-label, randomized controlled trial approved by the institutional review board of Shanghai Changhai Hospital and registered at ClinicalTrials.gov (NCT 04389333). All of the diagnostic and therapeutic modalities were carried out in accordance with the approved guidelines. Beginning on March 26, 2020, we consecutively recruited 40 patients in Changhai Hospital using predefined inclusion criteria and exclusion criteria. After fully understanding the procedure of ncMCE and this study, patients who gave informed consent were randomly assigned into ncMCE and MCE groups (in a 1:1 ratio) by using a stratified block randomization (fixed block size four). Randomization was based on a computer-generated list of random numbers using SPSS software (version 22.0, SPSS Inc., Chicago, Illinois, United States). Only after the enrolled participants completed all baseline assessments did the endoscopist inform them about their allocation. Eligible patients were adults (≥ 18 years of age) undergoing outpatient MCE. Patients with any of the following conditions were excluded: (1) dysphagia or symptoms of gastric outlet obstruction, suspected or known intestinal stenosis, overt gastrointestinal bleeding, fistulas and strictures; (2) history of upper gastrointestinal surgery or suspected delayed gastric emptying; (3) poor general condition, asthma or claustrophobia; (4) implanted metallic devices such as pacemakers, defibrillators, artificial heart valves or joint prostheses; (5) pregnancy or mental illness; (6) current participation in another clinical study; or (7) difficulty communicating.

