4 = very convenient; 3 = convenient; 2 = not sure; 1 = inconvenient; 0 = very inconvenient

12. How much time did you miss from work or regular activities due to the test?

4 = 0-2 hours; 3 = 3-4 hours; 2 = 5-6 hours; 1 = 7-8 hours; 0 = >8 hours

13. Do you think it is necessary to perform nc-MCE during the outbreak?

4 = very necessary; 3 = necessary; 2 = not sure; 1 = unnecessary; 0 = very unnecessary

14. Do you think the Nc-MCE put you to any inconvenience?

4 = definitely not; 3 = not; 2 = not sure; 1 = yes; 0 = definitely yes

15. Rate the overall acceptance of the test.

4 = very acceptable; 3 = acceptable; 2 = moderate; 1 = acceptable only in special situations; 0 = unacceptable

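### Chapter 8 calls any P<0.05 significant, but the plan does not define its secondary tests, label them exploratory or control multiplicity, and one secondary endpoint is a 15-item questionnaire with no total

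*Combined protocol and SAP*

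**What the plan says.** Chapter 8 (Statistical considerations) states: "All reported Pvalues are two-sided and differences that reached $P < 0.05$ were considered statistically significant". It makes no distinction between primary and secondary results. It names variance analysis, Kruskal-Wallis and Fisher's test without saying which outcome each serves.

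The same chapter gives the size of the trial: "As a pilot study to evaluate the feasibility and safety of ncMCE, the sample size was not calculated [19]", and "we planned to recruit 40 patients into two groups". With the 1:1 allocation in Section 3.1, that is 20 per arm.

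Section 4.3.1: "The primary endpoints were feasibility assessed by completion rate (CR) and safety evaluated by the occurrence of AE".

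Section 4.3.2: "Secondary endpoints included maneuverability score, pre-procedure perception and post-procedure satisfaction of patients, gastric examination time (GET), and diagnostic yield (DY").

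For maneuverability, Section 4.3.2 sets a minimum total of 4 and a maximum of 20, in the sentence that begins: "The score for each index was 1 to 5, with 1 as the worst and 5 as the best, respectively, and a total ranging from". Appendix 3 gives averaging rules for the signal and comfort indices.

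For the patient questionnaire (Appendix 2, Questionnaire 1) the plan gives no total, subscale or key item. The list runs from item 1 to "15. Rate the overall acceptance of the test".

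No section gives a multiplicity adjustment, a testing order, or a statement that secondary results are exploratory.

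**The concern.** The significance rule covers whatever P values are reported, and the plan does not say which those will be. For the patient questionnaire the only units defined are its items. The rule therefore allows a handful of tests on totals or two dozen tests on items and indices, and the choice can be made after the data are seen in an open-label trial.

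What is at stake is how secondary results are worded. With many comparisons in 40 patients, an isolated difference on comfort, convenience or a maneuverability index may well arise by chance. Under the present sentence it would be called statistically significant and could be read as a property of the remote system.

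**Working it through.** The plan states no family-wise error rate, so there is no figure to reproduce.

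**Inputs from the documents**
- Threshold: 0.05, two-sided, unadjusted (Chapter 8).
- Patients: 40 at 1:1, so 20 v 20 (Chapter 8; Section 3.1).
- Primary endpoints: completion rate and adverse events, 2 (Section 4.3.1).
- Maneuverability: 4 indices plus a total, 5 (Section 4.3.2; Appendix 3).
- Questionnaire 1: 15 items, no total (Appendix 2).
- Gastric examination time (GET) and diagnostic yield (DY), 1 each (Section 4.3.2).

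Maximum count: 2 + 5 + 15 + 1 + 1 = 24.

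**Step 1. Independent tests, all nulls true.** The chance of at least one false positive among k tests is 1 − 0.95^k.
- k = 24: 1 − 0.95^24 = 0.708, with 24 × 0.05 = 1.2 false positives expected.
- k = 22, without items 13 and 14, which are worded for ncMCE only: 0.676.
- k = 15, the items alone: 0.537.
- k = 6, one score per endpoint: 0.265. k = 7, with separate pre- and post-procedure totals: 0.302.

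**Step 2. The binary endpoints.** Fisher's test is conservative at 20 v 20. Its exact size at nominal 0.05 depends on the event rate, which the documents do not give:

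| Assumed rate in both arms | Actual size |
|---|---|
| 2% | 0.005% |
| 5% | 0.19% |
| 10% | 1.2% |
| 30% | 2.5% |
| 50% | 2.0% |

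The two primaries add almost nothing if technical failures and adverse events are rare. The calculations below assume 2% for failure to complete, 5% for adverse events and 50% for DY.

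**Step 3. Correlated items, all 24 tested.** Items within a questionnaire will be correlated, and the documents give no correlation. The simulation used 20 v 20 patients, ordinal answers, Kruskal-Wallis tests and one common factor per questionnaire, with 4,000 runs per setting. Three response patterns were assumed: spread out, 75% at the best score, and 95% at the best score. The table shows the chance of at least one false positive.

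| Correlation | Spread | 75% at best | 95% at best |
|---|---|---|---|
| 0 | 64% | 66% | 32% |
| 0.3 | 59% | 62% | 32% |
| 0.5 | 53% | 57% | 30% |
| 0.7 | 44% | 49% | 27% |
| 0.9 | 33% | 38% | 20% |

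A simpler simulation used normal test statistics for the 21 non-binary scores (15 items, 4 indices, their total, GET). It gave about 58%, 49% and 39% at correlations 0.3, 0.5 and 0.7. Across the two methods, leaving out the strong ceiling, the range at 0.3–0.7 is 39–62%.

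**Step 4. Totals only.** Take the patient total, the maneuverability total and GET at 5% each, and the three binary endpoints at their actual sizes:

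1 − 0.95³ × (1 − 0.0204) × (1 − 0.0019) × (1 − 0.00005) = 0.162.

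Splitting the patient total into pre- and post-procedure totals replaces 0.95³ with 0.95⁴ and gives 0.204. The simulated values over all settings run from 15% to 21%.

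**Step 5. Comparisons that are not clean nulls.** Appendix 3 fixes joystick strength at 5 for MCE, which feeds the comfort index and the total. A difference there could be built in and not due to chance. Removing those two scores and items 13 and 14 from the 21-score simulation gives 52%, 44% and 36% at correlations 0.3, 0.5 and 0.7.

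**Step 6. Direction.** The figures above count false results in either direction. The chance of at least one false result favouring ncMCE is 1 − 0.975^24 = 46% for 24 independent tests. In the 21-score model it is about 32%, 26% and 21% at the same three correlations.

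**The case against.** The strongest reply is that the plan never says each item is tested. Section 4.3.2 lists the patient questionnaire as one secondary endpoint, and Chapter 8 speaks only of P values that are reported. This stands. A reader might infer from Appendix 2 that all 15 items will be compared and that a false finding is therefore about as likely as not. The first part is a reasonable inference, because no total exists, but it is not written. The second depends on that inference and on assumed correlations and response patterns. The documents support only that the set of tests is undefined.

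A reader might also infer that the 5% rate fails for any single statement of significance. It does not. Each comparison keeps its own 5% rate, or less under Fisher's test. What is lost is control over the collection.

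Third, this is a pilot on feasibility and safety, and unadjusted P values for secondary scores are a common choice in a pilot. The primary conclusions are indeed barely touched. But Chapter 8 uses pilot status only to omit a sample size calculation, and then keeps plain significance wording for every P value. An exploratory label would answer the concern, and the plan has none.

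**Conclusion.** The point holds as a gap in definition and labelling. The plan applies one unadjusted threshold to an undefined set of secondary comparisons. The family-wise chance of a false significant result then depends on choices that the plan leaves open:

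- about 15–21% if only questionnaire totals are tested;
- 20–32% if all 24 are tested and answers sit at a strong ceiling;
- 39–62% if all 24 are tested at correlations of 0.3–0.7 without a strong ceiling;
- 71% for 24 independent tests at exactly 5%.

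Every figure assumes that all nulls are true, which is doubtful for the scores that include joystick strength. The correlations, response patterns and event rates are assumptions, not document values. Even the lowest figure is about three times the nominal 5%. The inflation comes almost wholly from the secondary scores, so it bears on how those are reported and not on completion rate or adverse events. It should be corrected.

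**What to change.** Replace the general P<0.05 sentence in Chapter 8. The new text should say that the secondary endpoints, and all questionnaire items and maneuverability indices, are exploratory. They are reported as between-group differences with 95% intervals and are not described as statistically significant. If the two primary endpoints are to be compared formally, the new text should keep a rule for them; this point asks for no change there.

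If the sponsor wants formal secondary tests, it should name them in advance and apply Holm's correction across them. Which ones is the sponsor's choice, since nothing in the documents favours a particular score. If a questionnaire total is intended, its scoring should be defined in Appendix 2.

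The cost is about two sentences in Chapter 8, with no change to data collection. Section 5.4 already provides for stating and justifying changes to the statistical plan. The downside is that fewer results can be called significant.
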